13.4.2 Bath Ankylosing Spondylitis Disease Activity Index (BASDAI)

The BASDAI consists of a 0 through 10 scale (0 being no problem and 10 being the worst problem, captured as a continuous VAS), which is used to answer 6 questions pertaining to the 5 major symptoms of AS:

1. How would you describe the overall level of **fatigue/tiredness** you have experienced?
2. How would you describe the overall level of **AS neck, back or hip pain** you have had?
3. How would you describe the overall level of pain/swelling in joints other than **neck, back, hips** you have had?
4. How would you describe the overall level of **discomfort** you have had from any areas tender to touch or pressure?
5. How would you describe the overall level of **morning stiffness** you have had **from the time you wake up?**
6. How long does your morning stiffness last from the time you wake up?

To give each symptom equal weighting, the mean (average) of the two scores relating to morning stiffness (questions 5 and 6) is taken. The resulting 0 to 10 number is added to the scores from questions 1-4. The resulting 0 to 50 score is divided by 5 to give a final 0 to 10 BASDAI score. Scores of 4 or greater suggest suboptimal control of disease, and subjects

with scores of 4 or greater are usually good candidates for either a change in their medical therapy or for enrollment in clinical trials evaluating new drug therapies directed at Ankylosing Spondylitis. BASDAI is a quick and simple index, taking between 30 seconds and 2 minutes to complete.

13.4.3 Bath Ankylosing Spondylitis Metrology Index (BASMI)

Cervical rotation

Cervical rotation is measured twice with the subject supine on plinth, head in neutral position, forehead horizontal (if necessary head on pillow or foam block to allow this, must be documented for future reassessments). Gravity goniometer placed centrally on the forehead. Subject rotates head as far as possible to the left, keeping shoulders still, ensure no neck flexion or side flexion occurs and the angle between the sagittal plane and the new plane after rotation is recorded. The better reading of the two is recorded. The same is repeated for the right side. Record the mean of the better reading from the right side and the better reading from the left side.

Tragus to wall distance

Tragus to wall distance is measured twice with the subject's heels and back rested against the wall. The chin should be at usual carrying level and the subject takes maximal effort to touch the head against the wall. The distance between the tragus and the wall is assessed and the better of the two assessments is to be reported.

Spinal lateral flexion (lumbar lateral flexion)

Subject stands with heels and buttocks touching the wall, knees straight, shoulders back, hands by the side. The subject is then asked to bend to the right side as far as possible without lifting the left foot/heel or flexing the right knee, and maintaining a straight posture with heels, buttocks, and shoulders against the wall. The distance from the third fingertip to the floor when subject bends to the side, is subtracted from the distance when subject stands upright. The better of two tries is recorded. The maneuver is repeated on the left side. Record the mean of the better reading from the right side and the better reading from the left side.

Lumbar flexion (modified Schober index)

Set marks in upright position 5 cm below and 10 cm above lumbosacral junction (spinal section of a line joining the dimples of Venus). Measure distraction of the marks when the subject bends forward as far as possible, keeping the knees straight. The better of two tries is recorded.

Maximal intermalleolar distance

Subject is lying down with the legs separated as far as possible with knees straight and toes pointed upwards. Alternatively, the subject stands and separates the legs as far as possible. The distance between medial malleoli is measured and the better of the two measurements is recorded.

Chest expansion

Chest expansion is measured with the subject hands resting on or behind the head. The measurement is taken at the fourth intercostal level anteriorly. The difference between maximal inspiration and expiration in cm is recorded twice and the better of the two measurements is reported.

Occiput-to-wall distance

Occiput to wall distance is measured twice with the subject's heels and back rested against the wall. The chin should be at usual carrying level and the subject takes maximal effort to touch the head against the wall. The distance between the occiput and the wall is assessed and the better of the two assessments is to be reported.

Table 16-1	Overview of analyses on major safety endpoints.....	30
Table 16-2	CTCAE grades for laboratory parameters to be analyzed	31
Table 16-3	Liver-related events.....	32
Table 16-4	Criteria for notable vital sign abnormalities.....	33
Table 19-1	Analysis visit windows (applied only for the core study).....	36
Table 19-2	Rules for flagging variables	38
Table 19-3	Examples for calculating exposure time for incidence rates (IR).....	43

List of abbreviations

AE	Adverse Event
ALT	Alanine Aminotransferase/ Glutamic Pyruvic Transaminase/ GPT
AS	Ankylosing Spondylitis
ASAS	Assessment of Spondyloarthritis International Society criteria
AST	Aspartate Aminotransferase/ Glutamic Oxaloacetic Transaminase/ GOT
BASDAI	Bath Ankylosing Spondylitis Disease Activity Index
BASFI	Bath Ankylosing Spondylitis Functional Index
BASMI	Bath Ankylosing Spondylitis Metrology Index
CI	Confidence Interval
CRO	Contract Research Organization
DMC	Data Monitoring Committee
ECG	Electrocardiogram
FAS	Full Analysis Set
GGT	Gamma Glutamyl Transferase
IA	Interim Analysis
IL	Interleukin
IRT	Interactive Response Technology
MCS	Mental Component Summary
MedDRA	Medical Dictionary for Regulatory Activities
MRI	Magnetic Resonance Imaging
PDS	Programming Data Specifications
PCS	Physical Component Summary
RA	Rheumatoid Arthritis

SAE	Serious Adverse Event
SCR	Screening
[REDACTED]	[REDACTED]
TNF	Tumor Necrosis Factor
TNF α -IR	TNF α Inhibitor Incomplete Responders
ULN	Upper Limit of Normal
VAS	Visual Analog Scale

1 Introduction

Data will be analyzed by Novartis according to the data analysis section 9 of the study protocol. The statistical methodology is described below and any deviations from the protocol are documented. Additional detailed information regarding the analysis methodology is contained in the Appendix section.

2 Changes to statistical methods planned in the protocol

MMRM modeling will be employed for all hierarchy continuous variables. Multiple imputation will be performed to impute the missing values [REDACTED] components in order to analyze the [REDACTED] inactive disease.

[figure not shown]
3 Study objectives

[figure not shown]
3.1 Primary objectives

The primary objective is to evaluate the sustainability of subject benefits as quantified by the ASAS20 (Assessment of SpondyloArthritis International Society criteria) in the whole study population during long-term (Week 260) treatment with secukinumab 75 and 150 mg provided as prefilled syringes.

3.2 Secondary objectives

1. To evaluate the sustainability of subject benefits in subjects with active AS as quantified by the ASAS40 response during long-term treatment with secukinumab 75 or 150 mg.
2. To evaluate the overall safety and tolerability of secukinumab in subjects with active AS.

4 Data presentation

Data analyses will be presented by treatment groups. For efficacy analysis the assigned and actual treatment will be displayed.

Unless otherwise stated, summary tables/figures/listings will be on all subjects included in the population under consideration.

Summary statistics for continuous variables will include N, mean, standard deviation, minimum, lower quartile, median, upper quartile, maximum. Summary statistics for discrete variables will be presented in contingency tables and will include absolute and relative frequencies.

For categorical or binary variables, the number and percent of subject in each category will be presented. The p-values, if presented, will be two-sided unless otherwise specified, and 95% CIs will be provided as appropriate.

In general, efficacy data from the extension study period will be reported for clinical study report (CSR) and publication(s). Efficacy tables and figures corresponding to the hierarchy assessments (e.g. ASAS20/40 responder analysis) will be presented from Week 1 in the core study up till the end of reporting period in the extension trial.

No formal hypothesis testing will be done. Hence, the p-values and CIs provided should be considered as exploratory only.

Safety data from core and extension studies will be reported cumulatively for CSR and publication(s). Placebo safety data from core will be reported only in the listings. For subjects who switched from placebo to secukinumab in core, their data prior to switch will not be reported.

All listings will be presented by treatment groups. All listings but the listings of deaths, non-fatal serious adverse events and adverse events requiring treatment discontinuation will display the placebo group followed by the indication of responder or non responder.

5 Subjects and treatments

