4.1 Inclusion criteria

Subjects eligible for inclusion in this study have to fulfill **all** of the following criteria:

1. Written informed consent must be obtained before any assessment is performed
2. Subjects must have completed the core study
3. Subjects who are deemed by the investigator to benefit from continued secukinumab therapy

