4.2 Exclusion criteria

Subjects fulfilling **any** of the following criteria are not eligible for inclusion in this study. No additional exclusions may be applied by the investigator, in order to ensure that the study population will be representative of all eligible subjects.

1. History of hypersensitivity to any of the study drugs or to drugs of similar chemical classes
2. Any subject who is deemed not to be benefiting from the study drug based upon lack of improvement or worsening of their symptoms
3. Use of any investigational drug except for secukinumab during the core study
4. Any subject taking other concomitant biologic immunomodulating agent(s) except secukinumab during the core study

5. Pregnant or nursing (lactating) women, where pregnancy is defined as the state of a female after conception and until the termination of gestation, confirmed by a positive hCG laboratory test.
6. Women of child-bearing potential, defined as all women physiologically capable of becoming pregnant, unless they are using effective methods of contraception during the entire study or longer if required by locally approved prescribing information (e.g., 20 weeks in EU). Effective contraception methods include:
 - Total abstinence (when this is in line with the preferred and usual lifestyle of the subject. Periodic abstinence (e.g., calendar, ovulation, symptothermal, post-ovulation methods) and withdrawal are not acceptable methods of contraception
 - Female sterilization (have had surgical bilateral oophorectomy with or without hysterectomy) or tubal ligation at least six weeks before taking study treatment. In case of oophorectomy alone, only when the reproductive status of the woman has been confirmed by follow up hormone level assessment
 - Male sterilization (at least 6 months prior to screening). For female subjects on the study, the vasectomized male partner should be the sole partner for that subject
 - Barrier methods of contraception: Condom or Occlusive cap (diaphragm or cervical/vault caps) with spermicidal foam/gel/film/cream/ vaginal suppository
 - Use of oral, injected or implanted hormonal methods of contraception or other forms of hormonal contraception that have comparable efficacy (failure rate <1%), for example hormone vaginal ring or transdermal hormone contraception
 - Placement of an intrauterine device (IUD) or intrauterine system (IUS)

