5.1 Analysis Sets

The following analysis sets will be used for the data analysis:

Extension Full Analysis Set (extension FAS): The extension FAS will be comprised of all subjects enrolled in the extension study.

(In this document extension FAS is referred to as FAS).

Of note, FAS will comprise only the subjects from extension whereas safety set will include from core or extension, safety set will be larger than FAS.

Up-titration Subset: The up-titration subset will be comprised of all subjects from the extension FAS set who received at least one dose of the up-titration dose.

[REDACTED]

Safety set: The safety set includes all subjects enrolled in the core study who took at least 1 dose of study treatment during the core study. Subjects will be evaluated according to treatment received.

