12.3 Handling of missing data

Missing data

Analysis of study data will be based on the observed data. In addition to the observed data approach, multiple imputation technique will be employed for the following binary variables: ASAS20, ASAS40, [REDACTED]

[REDACTED] Analysis will be limited to the higher originally randomized dose (AIN457 10 mg/kg - 150 mg)

For analyses of these parameters, if all post baseline values are missing then these missing values will not be imputed and this subject will be removed from the analysis of the corresponding variable, i.e. it might be that the number of subjects providing data to an analysis is smaller than the number of subjects in the FAS.

[REDACTED] mixed model repeated measures (MMRM) will be fitted assuming random missingness to assess the durability of secukinumab effect. The explanatory variables will be baseline score, weight,

TNF α status, analysis visit, and analysis visit by baseline score. An unstructured correlation matrix will be used thus allowing adjustment for correlations between time points within subjects. This analysis will be done on the entire treatment period for the AIN457 10 mg/kg - 150 mg treatment arm.

13 Analysis of the primary variable(s)

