13.2 Statistical model, hypothesis, and method of analysis

No formal hypotheses are proposed for this study. The proportion of subjects meeting the ASAS20 will be descriptively summarized for each treatment over time from week 1 in core study onwards and treatments will be compared by providing 95% CIs for the proportion of patients responding to treatment according to the ASAS20 criteria. Results will be presented for the FAS, as well as subgroups by TNF α status (naive or IR).

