14.1 Efficacy variables

Secondary [REDACTED] variables include:

- the proportion of subjects achieving ASAS40

For binary variables, the proportion of responders along with the 95% CI will be presented by groups according to the treatment sequence over analysis visits. For continuous variables, the change from core baseline will be summarized.

Results will be presented for the FAS, as well as subgroups by TNF α status (naive or IR) for the following variables: ASAS40, [REDACTED]

Graphical representation (line plots) regarding the response over time for the following measures will be provided in the observed data: ASAS20/40, [REDACTED]

[REDACTED] will also be graphically illustrated. The above mentioned figures will show the originally randomized AIN457 treatment groups.

Cumulative probability plots will be employed to display the change from baseline to week 208 illustrating the progression of subjects after 4 years [REDACTED]

Additional figures as in line plots, illustrating the up-titration effect of treatment will be created for the following parameters: ASAS20/40, [REDACTED]

ASAS20

The ASAS Response Criteria (ASAS20) is defined as an improvement of $\geq 20\%$ and ≥ 1 unit on a scale of 10 in at least three of the four main domains and no worsening of $\geq 20\%$ and ≥ 1 unit on a scale of 10 in the remaining domain.

The percentage of subjects experiencing ASAS20 response, followed by the respective 95% CI, will be presented by treatment sequence up to week 260 based on the observed data. The respective summaries will also be provided by TNF- α IR status.

Additional analysis will be based on the imputed responses only for the AIN457 150 mg group.

The percentage of subjects (and the 95% CI) experiencing ASAS20 response after up-titration will be presented in separate tables (observed data). Patients who had at least 1 dose of the up-titrated dose will be included.

[figure not shown]
ASAS40

[figure not shown]
The ASAS 40 response is defined as an improvement of $\geq 40\%$ and ≥ 2 units on a scale of 10 in at least three of the four main domains and no worsening at all in the remaining domain.

[figure not shown]
[figure not shown]
The percentage of subjects experiencing ASAS40 response, followed by the respective 95% CI will be presented by treatment sequence up to week 260 based on the observed data. The respective summaries will also be provided by TNF- α IR status.

[figure not shown]

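### Sustained ASAS20/40 response to Week 260 rests on observed data, and the only missing-data check covers one of four treatment sequences and, as written, stops at Week 156

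*SAP*

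**What the plan says.** **Main analysis.** SAP 13.1 makes ASAS20 over time to Week 260 the primary variable, on the FAS. SAP 14.1 says that the ASAS20 percentage and its 95% CI "will be presented by treatment sequence up to week 260 based on the observed data", and says the same for ASAS40. SAP 12.3 makes observed data the general rule.

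**Sensitivity analysis.** SAP 13.3 plans multiple imputation of ASAS20/40 to judge how robust the handling of missing data is. SAP 12.3 restricts it: "Analysis will be limited to the higher originally randomized dose", which is the 10 mg/kg - 150 mg arm. SAP 5.2 and 14.1 repeat the restriction. SAP 19.2.4 assumes MAR and gives 156 as the last visit imputed. Protocol 9.4.4 makes sensitivity analyses optional and names no method other than multiple imputation.

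**Population and start of the display.** SAP 4 says that the ASAS20/40 tables and figures "will be presented from Week 1 in the core study up till the end of reporting period in the extension trial". SAP 13.2 has ASAS20 "descriptively summarized for each treatment over time from week 1 in core study onwards", for the FAS. SAP 5.1 defines that set: "Of note, FAS will comprise only the subjects from extension whereas safety set will include from core or extension". Entry requires completion of the core study and applies to "Subjects who are deemed by the investigator to benefit from continued secukinumab therapy" (Protocol 4.1). Protocol 4.2 excludes "Any subject who is deemed not to be benefiting from the study drug based upon lack of improvement or worsening of their symptoms".

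**Where late assessments count.** After Week 104, SAP 7 and 19.1 use nominal visits only. Protocol 5.5.9, Protocol 5.5.11 and the footnotes to Tables 6-1 to 6-3 each describe the last on-treatment assessment, and not in the same terms.

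**The concern.** The study asks whether benefit is sustained. An observed-data rate at Week 260 describes the subjects still being assessed. If subjects who lose response tend to leave, the curve can stay flat while benefit in the enrolled cohort declines. A sensitivity analysis is meant to expose this. Here it is thinnest where it matters most: the late visits, the final time point and three of the four sequences. Imputation under MAR also presumes that a subject's earlier data explain the missing values, so it cannot show what happens if they do not. SAP 13.2 intends the treatments to be read against each other through their CIs, so unequal discontinuation between arms would also colour that reading.

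Two lesser matters bear on the same curve. Its first two years are conditional on a later entry decision that depends partly on response. And the week at which an early discontinuer's last assessment appears is not settled.

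**Working it through.** **1. Coverage by visit.** Protocol Tables 6-1 to 6-3 schedule patient global assessment and spinal pain after Week 104 at Weeks 116, 128, 140, 156, 168, 180, 192, 208, 220, 232, 244 and 260. (Rows for the other ASAS components are not visible in the public tables.) That is 12 visits. The imputation limit, read as Week 156, takes in 4. The other 12 - 4 = 8 (Weeks 168 to 260) lie beyond it.

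**2. Coverage by sequence.** SAP 5.2 lists four sequences: 10 mg/kg - 75 - 150 mg, 10 mg/kg - 150 mg, placebo - 75 - 150 mg and placebo - 150 mg. Imputed results are reported for one. Of 12 x 4 = 48 sequence-by-visit results after Week 104, 4 x 1 = 4 have a specified sensitivity analysis. Extending the imputation to Week 260 in that one arm would give 12 of 48. The imputation starts at Week 1, so it is not specific to the extension.

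**3. Possible size.** Let r be the observed rate, d the share discontinued among subjects either assessed or discontinued, and m the response rate the discontinued would have had. The overstatement is

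r - [(1 - d) r + d m] = d (r - m).

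For given r and d it is largest at m = 0, where it equals d x r. The documents give none of these values for the extension, so all are assumed.

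| r | d | m | Overstatement |
|---|---|---|---|
| 60% | 10% | 0 | 6 points |
| 60% | 20% | 0 | 12 points |
| 80% | 10% | 0 | 8 points |
| 80% | 20% | 0 | 16 points |
| 70% | 20% | 30% | 8 points |
| any | any | equal to r | 0 |

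**4. Weeks 1-104.** Protocol 9.7 expects 279 to 316 entrants, being 75% to 85% of the core study. Core N is not in the available text. Back-solving gives 279/0.75 = 372.0 and 316/0.85 = 371.8, so about 372. Check: 0.75 x 372 = 279.0 and 0.85 x 372 = 316.2, which reproduces the stated range. Subjects outside the FAS: 372 - 316 = 56 (15.1%) to 372 - 279 = 93 (25.0%). These are planning figures. Non-entrants' response is not given, so the effect on the curve cannot be derived. If they responded as entrants did, it is 0.

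**5. Nominal week of the last assessment.**
- Protocol 5.5.9, straight after a sentence on subjects who stop treatment, places the Week 260 assessments 4 weeks, and F268 12 weeks, after the last dose for subjects remaining in the trial. For completers this fits exactly: last dose Week 256 (Protocol 5.5.11), 256 + 4 = 260 and 256 + 12 = 268.
- Protocol 5.5.11 and all three table footnotes tie the visit to the end of the subject's current period (Week 156, 208 or 260).
- SAP 19.1 counts it wherever the nominal label falls.

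Example: last dose at Week 120, assessment at Week 124. Under the footnotes it is labelled Week 156, which is 156 - 124 = 32 weeks later than it was made. Under a literal reading of 5.5.9 it is labelled Week 260, which is 136 weeks later.

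**The case against.** **The limit of 156 may be a leftover.** SAP 14.1 places the imputed analysis directly after results to Week 260, so the intention is probably to impute to Week 260. That is a fair reading. But SAP 19.2.4 is the specification that will be programmed, the two sections disagree, and settling them leaves three sequences and the MAR assumption untouched.

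**The study is descriptive.** There are no hypotheses, and SAP 4 calls the CIs exploratory. This stands: no error rate is affected. It limits the weight of the point but does not remove it, since the descriptive rate is the primary result.

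**Imputation by group is awkward where doses were escalated.** True for the 75 mg sequences, although the SAP does not give this reason and the placebo - 150 mg sequence, which has no escalation, is left out too. A non-responder row needs no model.

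**Disposition is reported.** SAP 8.1 tabulates discontinuations and reasons. This shows attrition but does not connect it to response at a visit.

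**Stronger readings that the documents do not support.** A reader might infer that the SAP conceals the selection of extension entrants. It does not: SAP 5.1 says twice that the FAS is the extension set, and SAP 13.2 names the FAS in the sentence after the Week 1 display. Following one cohort from Week 1 is also a coherent way to show sustainability. A reader might take the line-plot sentence in SAP 14.1, "The above mentioned figures will show the originally randomized AIN457 treatment groups", as a claim that all randomised subjects are shown. It says which arms are plotted. A reader might infer that Week 260 will be filled with early assessments. One ambiguous sentence in Protocol 5.5.9 stands against Protocol 5.5.11 and three footnotes, so this is a text to reconcile, not an established defect.

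**Conclusion.** The gap in the sensitivity analysis is real. As written, the primary result at Weeks 168-260 has no specified missing-data check in any arm, three sequences have none at any visit, and departure from MAR is not examined anywhere in the available text. Observed-data rates could overstate sustained benefit by up to 6 to 16 points under the assumed ranges. The true amount depends on discontinuation and on response among those who leave, which the documents do not give. It is 0 if leavers would have responded as stayers do.

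The Week 1-104 point is secondary. The set is disclosed; what is missing is a statement on the outputs that these rates are conditional on core completion and judged benefit. About 56 to 93 of about 372 core subjects are outside the set on planning figures. A reader might infer a known upward bias in the early curve. The direction is plausible, but its size cannot be derived and may be 0.

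The nominal-week point is a reconciliation of wording.

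Statements of absence apply to the available text only: table shells are not supplied, and parts of SAP 5.1 and 12.3 are redacted.

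**What to change.** **Main changes**
- (a) In SAP 19.2.4, change the last imputed visit from 156 to Week 260, in line with SAP 14.1.
- (b) In SAP 13.3, add for all four sequences at Weeks 116-260 a sensitivity row on the extension FAS that counts discontinued subjects as non-responders, beside the observed-data rate. Keep the observed-data rule for a missed visit in a subject still on study, so that the two rows differ only through discontinuation. Dose escalation is not discontinuation: those subjects stay in their sequence with their assessed response.

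**Secondary changes**
- (c) In SAP 4 and 13.2, title the Week 1-104 results *Subjects who entered the extension* and show N assessed per visit, including on line plots.
- (d) Reconcile Protocol 5.5.9 with Protocol 5.5.11 and the footnotes to Tables 6-1 to 6-3. State in SAP 19.1 at which nominal week early discontinuers' end-of-treatment assessments count. Row (b) depends on this.

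**Cost.** Low. (a), (c) and (d) are mostly wording. (b) adds one row per endpoint and sequence from data already collected. Its drawback is that administrative exits count as failures, so it should be reported as a sensitivity row only.

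A Week 1-104 display of all subjects randomised in the core study is optional. It would need an efficacy set that the available SAP text does not define.
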